8.2 ANALYSES POPULATIONS

Subjects that are screened but disqualified based on the preoperative and intra-operative eligibility criteria will be excluded from the safety and effectiveness data analyses. However, their reasons for the screen failure will be summarized. The analyses populations defined below are defined for the study lens. For the fellow-eye cohort (Cohort 4), data analyses for some selected outcomes (such as [REDACTED] safety events, UCDVA, and BCDVA) may be performed for eyes with successful IOL implants during surgeries in order to numerically compare to the results of the HMIOL cohorts.

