 15. Taking systemic medications that, in the opinion of the investigator, may confound the outcome or increase the risk to the subject (e.g. Tamsulosin Hydrochloride – Flomax) or other medications including anticholinergics, alpha adrenergic blocking agents with similar side effects (e.g. small pupil/floppy iris syndrome)
- 3.2.3 EXCLUSION CRITERIA DURING SURGERY
1. Vitreous loss prior to use of the investigational device
 2. Positive posterior pressure preventing safe implantation of the lens system
 3. Anterior chamber hyphema preventing visualization of implantation
 4. Any zonular or capsular rupture or capsular bag instability

CLARVISTA MEDICAL

PROTOCOL CP-00001 Rev.05

5. Intraoperative miosis preventing visualization of fixation features
6. Need for concomitant procedures (e.g. glaucoma surgery, LRI, RK, LASIK, etc.)
7. Subject who, in the clinical judgment of the investigator, is not suitable for participation in the study for another clinical reason, as documented by the investigator

3.2.4 EXCLUSION CRITERIA – 3 MONTHS POST-PRIMARY CATARACT EXTRACTION (AFFECTING ELIGIBILITY FOR HMIOL OPTIC EXCHANGE)

1. Any clinical finding or intraocular complication during primary cataract extraction that (in the judgment of the Investigator) is likely to increase complications with optic exchange procedure or present undue risk to the subject (e.g. unexplained endothelial cell loss, post-primary cataract extraction macular edema, persistent ocular inflammation, etc.)
2. Presence of YAG Capsulotomy in the primary (HMIOL) eye

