3.3.2 DAY 0 VISIT (PRIMARY CATARACT EXTRACTION SURGERY)

Record any changes in concomitant medications and medical history, prepare the subject for surgery in the study eye (see Surgical Procedure Guide), and re-review inclusion/exclusion criteria to ensure subject still qualifies to participate.

The Investigator will carry out the surgical procedure and HMIOL implantation as specified in the Surgical Procedure Manual and the following details will be captured in both Source Documents and eCRFs:

- Date of surgery
- Operative eye
- Test or Fellow Eye
- Incision location and size

CLARVISTA MEDICAL

PROTOCOL CP-00001 Rev.05

- Capsulorhexis size
- Ophthalmic Viscoelastic Device (OVD) used
- All medication used pre-, intra-, and post-operatively (ophthalmic and systemic)
- Surgical times
- Model, serial number, and diopter of HMIOL implant components
- IOL injection device

Once the subject is confirmed stable post-surgery, provide IRB / EC approved post-operative instructions and discharge.

Record any AEs, adverse device effects (ADEs), unexpected adverse device effects (UADEs), or device deficiencies (DD) (see Sections 6.1.1, 6.1.2, 6.1.3, or 6.1.4 respectively) observed pre-, intra-, or post-operatively.

In the event the subject is not implanted with an HMIOL device due to an intra-operative complication, the subject will be discontinued (see Section 4.5).

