6.2 AE EVALUATION

AEs experienced in this study may be associated with the study device (i.e. ADE) or the study protocol as demonstrated in the following non-exhaustive list of examples:

Study Device (ADE)

- IOL dislocation
- Explant due to haptic break/damage
- Explant due to base and/or optic damage

Study Protocol

- Allergic reaction to dilating drops
- Lens remnants following surgery
- Capsular tear during surgery to implant study device

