8.2.1 SAFETY POPULATION

The **Safety** Population includes eyes with attempted study lens (HMIOL) implantation, (successful or aborted after contact with the eye). The intraoperative and postoperative AEs and DDs will be summarized based on the safety population.

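### Protocol sections 8.2 and 8.2.1 give opposite rules for the safety analysis of eyes that meet an intra-operative exclusion criterion after the HMIOL has contacted the eye

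*Protocol*

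**What the plan says.** Four places in the protocol bear on this point.

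- **Section 8.2** opens the analysis populations with a general rule. Screened subjects who are "disqualified based on the preoperative and intra-operative eligibility criteria will be excluded from the safety and effectiveness data analyses"; only the reasons for their failure are to be summarized.
- **Section 3.2.3** lists the criteria applied during surgery. The first is limited in time: "Vitreous loss prior to use of the investigational device". The fourth is not: "Any zonular or capsular rupture or capsular bag instability".
- **Section 8.2.1** defines the Safety Population as eyes with an attempted HMIOL implantation, whether "successful or aborted after contact with the eye". It adds: "The intraoperative and postoperative AEs and DDs will be summarized based on the safety population".
- **Section 6.2** gives "Capsular tear during surgery to implant study device" as an example of an adverse event associated with the study protocol.

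Section 3.3.2 adds: "In the event the subject is not implanted with an HMIOL device due to an intra-operative complication, the subject will be discontinued". It also asks for events seen during surgery to be recorded.

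**The concern.** Take an eye in which the capsule or zonules rupture while the HMIOL is being inserted or assembled, and the implantation is abandoned. Section 8.2.1 counts it. Section 8.2, read with the fourth criterion of section 3.2.3, leaves it out of the safety analyses and keeps only a reason for failure.

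The primary objective in section 2.0 is the feasibility of HMIOL implantation and assembly, and eyes in which the attempt failed after contact are direct evidence on it. Excluding an eye that had the event takes one from both numerator and denominator, so the reported rupture rate can only fall. If the choice between the two rules is left until the events are known, it can also look driven by the results.

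**Working it through.** The plan states no figure on this point, so there is none to reproduce. The check has two parts: a comparison of the rules case by case, and an illustration of size.

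**Comparison of the rules**

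| Eye | Section 8.2 with 3.2.3, read literally | Section 8.2.1 |
|---|---|---|
| Criterion met before the HMIOL contacts the eye; no implantation | Excluded from safety | Not in the Safety Population |
| Rupture after contact; implantation aborted | Excluded from safety | In the Safety Population |
| Rupture after contact; HMIOL still implanted | Excluded, if treated as disqualified | In the Safety Population |

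The rules agree in the first row. They conflict in the second, and in the third if such an eye is treated as disqualified.

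The conflict depends on the fourth criterion applying after contact. The first criterion carries an explicit limit to the time before device use and the fourth does not, so a literal reader has no ground for adding one. Section 4.5 does not help: it lists posterior capsular rupture among the complications, described there as unrelated to the device, that prevent implantation and lead to discontinuation. It does not say how such eyes are analysed.

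**Size, for illustration**

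Inputs: the number of attempted eyes n and the number of ruptures after contact k. Both are assumptions, because the documents give no rupture rate. The values of n lie in or near the planned range of 100 to 200 eyes (protocol synopsis, Sample Size). All k implantations are assumed aborted, with no other rupture in the study.

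- Counted (8.2.1): the rate is k/n. The exact one-sided upper 95% limit is the value p that solves P(X ≤ k | n, p) = 0.05, that is, the 0.95 quantile of a Beta(k + 1, n − k) distribution.
- Excluded (literal 8.2): the rate is 0/(n − k). The upper limit is 1 − 0.05^(1/(n − k)).

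For k = 2 and n = 107:

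- Counted: 2/107 = 1.9%; the 0.95 quantile of Beta(3, 105) is 5.8%.
- Excluded: 0/105 = 0%; 1 − 0.05^(1/105) = 2.8%.

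Other assumed values:

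| k / n | Rate if counted | Upper limit if counted | Excluded | Upper limit if excluded |
|---|---|---|---|---|
| 1/100 | 1.0% | 4.7% | 0/99 | 3.0% |
| 3/100 | 3.0% | 7.6% | 0/97 | 3.0% |
| 5/100 | 5.0% | 10.2% | 0/95 | 3.1% |
| 2/200 | 1.0% | 3.1% | 0/198 | 1.5% |
| 5/200 | 2.5% | 5.2% | 0/195 | 1.5% |

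Under exclusion the limit hardly moves with k, because the events are no longer in the data.

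**Which analyses are affected**

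SAP Table 1 lists the ISO events with a safety and performance endpoint (SPE) rate. Capsular and zonular rupture are not among them, so there is no SPE comparison for rupture to distort. The effect is on the general adverse event rates and on the intra-operative events, which SAP section 5.5 tabulates separately.

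**The case against.** The strongest reply is that the two sections can be read together without conflict. The 8.2 sentence speaks of screened subjects and calls their exclusion a screen failure. Section 3.3.1 treats a subject who meets all criteria as enrolled before surgery, and sections 3.3.2 and 4.5 treat a subject who is not implanted as discontinued, which is a different category. Section 8.2 then introduces the populations defined below it, and 8.2.1 names exactly the eyes and outcomes at issue. On ordinary principles a specific definition governs a general introduction. Sections 3.3.2, 6.1.1 and 6.2 and SAP section 5.5 all show an intention to record and report such events.

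Much of this stands, and it makes 8.2.1 the likely intention. It does not remove the conflict. Section 8.2 expressly includes intra-operative criteria, which can only apply after the enrolment described in 3.3.1, so the sentence reaches past ordinary screening. No sentence available for review says that 8.2.1 prevails.

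A reader might infer that the plan removes device-caused ruptures from the safety data. The documents do not support that: 8.2.1 says the opposite, and exclusion follows only if 8.2 is allowed to override it. A reader might also infer that the SAP repeats the problem. That cannot be judged. The SAP says that its analyses supersede those in the protocol, but its Safety Population definition is not in the text available for review. It may already settle the matter, and its absence here is not a fault in the plan.

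**Conclusion.** The concern holds as an unresolved inconsistency between protocol section 8.2, read with the fourth criterion of 3.2.3, and section 8.2.1. It affects eyes that meet an intra-operative exclusion criterion after contact with the HMIOL. Under one of the two stated rules, ruptures after device contact could drop out of the general and intra-operative adverse event rates.

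The size cannot be known from the documents. In the 2-in-107 illustration, exclusion alone takes the upper limit to about half its value. This rests on the assumed count, on all affected implantations being aborted, and on 8.2 overriding 8.2.1. It should not be read as a forecast of bias.

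Severity is moderate. The probable intention is sound and the study's tests are not meant for definitive regulatory conclusions, but the ambiguity touches the primary objective and is easily removed.

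**What to change.** 1. In protocol section 8.2, limit the exclusion from the safety analyses to subjects disqualified before any HMIOL component contacts the eye.
2. Add that section 8.2.1 governs every eye with HMIOL contact, whichever intra-operative criterion is met afterwards.
3. Confirm that the SAP's Safety Population definition says the same, and align it if it does not.
4. Reconcile 3.2.3 with 8.2 for analysis purposes only. The surgical eligibility rule need not change, and this point takes no position on it.

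The cost is a sentence or two in the protocol and, if needed, one in the SAP. Section 3.3.2 already requires intra-operative events to be recorded, so no new data are needed. The downside for the sponsor is that reported safety rates may be slightly less favourable. The wording should be settled before the analysis.

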8.3.2.1 BCDVA

The LogMAR will be derived for BCDVA. The descriptive statistics for continuous variables will be used to summarize LogMAR BCDVA at each visit based on the implanted-eye population for the three different lens cohorts (HMIOL Cohort 1, HMIOL Cohort 2, and Fellow-eye Cohort). The data at preoperative and 3-month post-primary-surgery will also be summarized for the HMIOL-eye cohort.

Additionally, the number and percentage of eyes reaching BCDVA 20/40 or better at each visit will be prepared for Cohort 1, Cohort 2, and the Fellow-eye Cohort. The one-sided upper 95% confidence limit of the proportion of HMIOL eyes with 20/40 or better will be calculated based on the binomial distribution and compared to a target of 0.925. If the confidence limit is > 0.925 , then the null hypothesis of $p \geq 0.925$ will not be rejected.

The analyses will be repeated based on the Per Protocol Population and the Best-case Population.

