8.3.2.4 ERROR PREDICTED REFRACTION (EPR)

The error predicted refraction (EPR) will be calculated for each treated eye as follows:

EPR = Postoperative MRSE adjusted to 6 meters – TRRE (target residual refractive error)

Then the absolute value of EPR will be derived. The means, standard deviations, minimum, and maximum of absolute EPR at each visit will be provided for all three lens cohort based on Implanted-eye Population. Additionally, the number and percentage of eyes with an EPR within ±0.50 D of target and of ±1.00 D of target will be derived for each postoperative visit.

For the HMIOL-eye Cohort and HMIOL Cohort 1, the difference in the absolute EPR between the HMIOL eye and its fellow eye at the same postoperative visits will be calculated for each subject. The mean, standard deviation, minimum, and maximum of the difference will be derived along with the 95% confidence interval of the mean difference.

For the HMIOL Cohort 2, the difference in the absolute EPR will be compared to the 3 month pre exchange EPR for the same eye at all postoperative visits. The mean, standard deviation, minimum, and maximum of the difference will be derived along with the 95% confidence interval of the mean difference.

[REDACTED]

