1 TITLE PAGE

Protocol Number:	ClarVista CP-00001
Medical Specialty:	Surgical
Project Name /Number:	NA
Sponsor Name & Address:	CLARVISTA MEDICAL, INCORPORATED [name] [name] [contact] [contact]
Test Article(s) / Product(s):	ClarVista HARMONI® Modular Toric Intraocular Lens System

Protocol CP-00001

ClarVista Medical, Inc.

Statistical Analysis Plan for Protocol CP-00001

Sponsor

ClarVista Medical, Incorporated
[name]
[name]
[contact]
[contact]

Original Version Date

24 February 2017

Protocol CP-00001

ClarVista Medical, Inc.

Table of Contents

1. Purpose	3
2. Scope.....	3
3. Software.....	3
4. Design and Objectives.....	3
5. Statistical Analyses.....	4
6. Sample Size	7
7. Analysis Populations	7
8. Sensitivity Analyses.....	8
9. Subgroup Analyses.....	8
	
11. Deviations from the Statistical Analysis Plan.....	9
12. References	9

Protocol CP-00001

ClarVista Medical, Inc.

1. Purpose

This Statistical Analysis Plan documents and describes the planned analyses for the CP-00001 CLEAR study. This is a feasibility study of the ClarVista HARMONI Modular Intraocular Lens System for the Treatment of Aphakia Following Cataract Surgery.

The intent of the study is to demonstrate the

- Feasibility of HARMONI IOL (HMIOL) implantation and assembly in subjects undergoing cataract surgery
- Feasibility of the HMIOL optic component exchange procedure (performed 3 months following primary cataract extraction)

Safety and effectiveness of these procedures will be characterized with the intent of supporting a future confirmatory study.

2. Scope

This document is based on the Investigational Plan CP-00001, Rev.05. Changes to the Investigational Plan may require updates to this document. Analyses described here expand on and supersede those described in the Investigational Plan.

3. Software

Statistical analyses will be performed with SAS System Software version 9.4 or above (SAS Institute, Cary, N.C.), R version 3.3 or above (R Core Team, <http://www.R-project.org>), or other validated statistical software package.

4. Design and Objectives

The CP-00001 study is designed as a prospective, multi-center, cohort study. Any pre-planned formal hypothesis tests for this feasibility study are not for the purposes of generating definitive conclusions to support regulatory approval.

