Several cohorts of subjects are specified to help characterize the clinical significance of the study outcomes in eyes with and without optic exchange. These cohorts are defined as follows:

All HMIOL Eyes Cohort: Defined as all study eyes implanted with the study device. Analysis of follow-up visits for this cohort definition is restricted to 1 Day, 1 Week, 1 Month, and 3 Months following primary cataract extraction (PCE).

Cohort 1: Defined as the subset of study eyes implanted with the study device without a subsequent optic exchange procedure. Analysis of follow-up visits for this cohort definition is restricted to 1 Day, 1 Week and 1, 3, 6 and 12 Months following primary cataract extraction.

Cohort 2: Defined as the subset of study eyes implanted with the study device with a subsequent optic exchange procedure. Analysis of follow-up visits for this cohort will cover two time periods:

- Pre-Optic Exchange, comprising 1 Day, 1 Week, 1 Month, and 3 Months following primary cataract extraction, prior to the optic exchange visit.
- Post-Optic Exchange, comprising 1 Day, 1 Week, 1 Month, 3 Months, 6 Months, and 12 Months following optic exchange. The baseline for the post-optic exchange visits is the 3 Month pre-optic exchange visit.

Fellow Eyes Cohort: Defined as the contralateral eyes not implanted with the study device. Analysis of follow-up visits for this cohort definition is restricted to 1 Day, 1 Week, 1 Month, 3 Months, 6 Months, and 12 Months following primary cataract extraction.

Separate analyses are planned for each cohort.

Protocol CP-00001

ClarVista Medical, Inc.

5. Statistical Analyses

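### Acuity in HMIOL and fellow eyes is compared through separate cohort summaries: Cohort 1 and Cohort 2 are read against other people's eyes, and the all-eyes comparison lacks a paired interval

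*Protocol*

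**What the plan says.** Each subject is to receive the HMIOL in one eye and a commercial lens in the other (protocol 3.1), with fellow-eye follow-up on a parallel schedule (protocol 3.3.3; Appendix A, Tables 1 and 2).

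- **Purpose of the fellow-eye data.** Protocol 8.2 makes fellow-eye analysis of selected outcomes, among them UCDVA and BCDVA, optional, "in order to numerically compare to the results of the HMIOL cohorts".
- **BCDVA.** Protocol 8.3.2.1 summarises logMAR BCDVA by cohort at each visit. It also plans counts and proportions at an acuity threshold, again by cohort: "eyes reaching BCDVA 20/40 or better at each visit will be prepared for Cohort 1, Cohort 2, and the Fellow-eye Cohort". For all HMIOL eyes together it adds: "The data at preoperative and 3-month post-primary-surgery will also be summarized for the HMIOL-eye cohort".
- **SAP.** Section 4 defines the Fellow Eyes Cohort without splitting it by optic exchange ("Defined as the contralateral eyes not implanted with the study device") and says "Separate analyses are planned for each cohort". Section 5.6 lists fellow-eye BCDVA and UCDVA as endpoints in their own right. Section 5.1 promises a 95% confidence interval for changes from earlier visits, which does not cover a difference between eyes. Section 2 gives the SAP precedence: "Analyses described here expand on and supersede those described in the Investigational Plan".
- **Pairing elsewhere.** For the HMIOL-eye Cohort and Cohort 1, protocol 8.3.2.4 says "the difference in the absolute EPR between the HMIOL eye and its fellow eye at the same postoperative visits will be calculated for each subject", with a mean, SD and 95% confidence interval.

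**The concern.** The fellow eye is the only concurrent comparator, and the plan pairs the two eyes for refractive accuracy but not, in the legible text, for acuity. Two separate consequences follow.

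First, Cohorts 1 and 2 are formed at 3 Months, largely on whether the study eye's outcome was satisfactory and whether the subject chose exchange (protocol synopsis and 3.3.4). They are different, outcome-selected people. Reading either cohort against the fellow eyes of everyone lets differences between people look like differences between lenses.

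Second, where the people are the same, two marginal means and SDs do not give the precision of their difference, because the between-eye correlation is not reported. The study is meant to inform a confirmatory trial. The between-eye acuity difference and its SD are useful planning quantities that these tables would not provide.

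**Working it through.** **Plan's own figure.** The documents give no sample size, power or precision for an HMIOL-versus-fellow acuity comparison. The only BCDVA power figure is for the one-sample test against 0.925 (protocol 8.1). With an exact binomial at n = 100, H0 is rejected at 87 or fewer successes (exact alpha 0.0364), and power at p = 0.85 is 0.7527, matching the stated 0.753. All eight table rows reproduce. This figure does not bear on the present point.

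**Inputs.** 105 subjects and 44 exchanges come from the early-termination list in protocol 4.7.1. They are one scenario, since enrolment may reach 200. The acuity SD, the between-eye correlation r and any cohort difference in fellow eyes are not in the documents, so ranges are assumed.

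**Step 1: who is in the fellow-eye column.** Cohort 1 has 105 − 44 = 61 subjects.
- Beside Cohort 1, the share from other people is 44/105 = 42%.
- Beside Cohort 2, it is 61/105 = 58%.
- For all HMIOL eyes up to 3 Months, it is essentially nil.

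**Step 2: what the mixing could do.** Shift in the apparent contrast = share from other people × D, where D is the assumed difference in mean logMAR between the two cohorts' fellow eyes. The direction is unknown.

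| D | Cohort 1 shift | Cohort 2 shift |
|---|---|---|
| 0.02 | 0.008 | 0.012 |
| 0.05 | 0.021 | 0.029 |
| 0.10 | 0.042 | 0.058 |

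**Step 3: precision, all HMIOL eyes.** Unpaired SE = SD × √(2/n); paired SE = SD × √(2(1 − r)/n); ratio = √(1 − r). With an assumed SD of 0.10 logMAR and n = 105, the unpaired SE is 0.10 × √(2/105) = 0.0138.

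| Assumed r | Ratio | Paired SE |
|---|---|---|
| 0.3 | 0.84 | 0.0115 |
| 0.5 | 0.71 | 0.0098 |
| 0.7 | 0.55 | 0.0076 |

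**Step 4: precision, Cohort 1.** The 95% half-widths below are in SD units.
- Own-fellow pairs, 1.96 × √(2(1 − r)/61): 0.297, 0.251 and 0.194 for r = 0.3, 0.5 and 0.7.
- Pooled column treated as independent, 1.96 × √(1/61 + 1/105): 0.316.
- Pooled column with the overlap handled correctly, 1.96 × √(1/61 + 1/105 − 2r/105): 0.279, 0.251 and 0.220.

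So in the exchange cohorts the argument for same-subject columns is mainly who is being compared. Precision improves over a correctly handled pooled column only when r exceeds 0.5.

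**Step 5: which visits can be paired.** Fellow-eye BCDVA is scheduled at 1, 3 and 12 Months (Table 2), and HMIOL BCDVA is scheduled at those visits too (Table 1). After exchange, Cohort 2 visits restart. Exchange falls on Day 81 to 121 (3 Month Visit at Day 80–100, plus 1–21), so its 3-month visit is Day 161 to 221. Fellow-eye surgery falls on Day 7 to 30, so, reading Table 2 days from that surgery, the fellow 3-month visit is Day 87 to 130. Visits with the same label are then not at the same time.

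**The case against.** The strongest reply is that nothing depends on this comparison. It is optional, it is numerical, and the study is a feasibility study. BCDVA is judged against a fixed 0.925, not against fellow eyes. The SAP takes precedence, and its legible text lists fellow-eye acuity without any formal contrast. All of that stands, and it limits the weight of the point.

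Four stronger readings are tempting and are not supported:

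- **That the whole comparison mixes different people.** It does so only for Cohort 1 and Cohort 2. For all HMIOL eyes at 3 Months, with complete data, the difference in means equals the mean paired difference.
- **That a planned result, test or power figure is invalid.** The plan never computes the unpaired SE used above. The ratios show what a paired interval would add over what a reader could work out from the marginal tables.
- **That no paired acuity analysis exists anywhere.** Parts of protocol 7.2, 8.3.2 and 8.3.2.4, and SAP text after the Fellow Eye Cohort endpoints and around section 10, are blacked out or absent. The statement is confined to what can be read.
- **That pairing isolates a lens effect.** The investigator chooses the study eye, partly on target refraction, and that eye is operated on first. Fellow eyes may later have refractive surgery or lens exchange (protocol 3.3.3). Pairing removes differences between subjects, not these.

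**Conclusion.** The point holds as a modest, inexpensive improvement to a descriptive analysis. In the legible text, acuity in HMIOL and fellow eyes is set side by side as separate cohort summaries, although the pairs exist by design and are used for absolute EPR.

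In the 105/44 scenario, 42% of the fellow eyes beside Cohort 1 and 58% of those beside Cohort 2 belong to other people. These shares change with enrolment and exchange rate. Whether the mixing moves the result depends on an unknown difference between the cohorts' fellow eyes. For all HMIOL eyes up to 3 Months only precision is lost, by a factor of √(1 − r), which rests on an assumed correlation and similar SDs in the two eyes. No stated power, test or success rule is wrong.

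**What to change.** In protocol 8.3.2.1 and SAP 5.6:

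1. Add the within-subject HMIOL-minus-fellow difference in logMAR BCDVA (mean, SD, 95% confidence interval) and the paired difference in percent 20/40 or better, with a 95% interval suited to paired proportions. Make all HMIOL eyes at 3 Months the main comparison and 1 Month supporting. Add 12 Months for Cohort 1.
2. Show Cohort 2 after exchange only under a stated visit-matching rule.
3. Do the same for UCDVA in pairs where both eyes' recorded target is distance, and define that condition in the SAP.
4. In the Cohort 1 and Cohort 2 tables, restrict the fellow-eye column to the same subjects with data at that visit. Keep the existing marginal summaries alongside.
5. State that pairing removes between-subject differences but not the investigator's choice of study eye or the order of surgery.

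No new data are needed. The cost is wording and a little more programming. Pairs with one eye missing at a visit drop out of the paired rows, which is why the marginal summaries should stay.
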